3.3.6 Systemic Corticosteroid Dose

The systemic corticosteroid dose will be evaluated at baseline and on Days 7, 14, 21, 28, 56, 86, 6 months and 12 months post-randomization.

3.3.7 CMV-Reactivation

The proportion of patients requiring new systemic treatment for an increasing CMV PCR level per institutional practice for CMV-reactivation will be evaluated at Day 56 post-randomization. Patients receiving only standard of care viral prophylaxis will not be included in this assessment.

3.3.8 Patient-Reported Outcomes

Patient-reported outcomes for both adolescents and adults will be assessed at baseline, Days 28, 56 and 180 post-randomization by the MD Anderson Symptom Inventory⁸⁵ (MDASI), and selected Patient-Reported Outcome Measurements Information System (PROMIS) subscales for gastrointestinal symptoms, physical function and satisfaction with participation in social roles. Adolescent versions should be completed by patients who are less than 18 years of age at the time of enrollment. The instruments will be scored according to the recommendations of the developers. Patient-reported outcomes (PRO) data will be collected electronically. The MDASI instrument will only be offered to English- and Spanish-speaking patients. The PROMIS instrument will only be offered to English-speaking patients. The instruments cannot be completed by surrogates.

CHAPTER 4

4 PATIENT ENROLLMENT AND EVALUATION

4.1 Approaching Patients, Eligibility Screening and Obtaining Consent

Patients with previously untreated, acute GVHD meeting eligibility criteria will be approached as soon as possible after diagnosis. Patients willing to participate in the trial will sign a NMDP IRB-approved consent or assent form, and eligibility for enrollment will be further evaluated.

4.2 Enrollment and Randomization

Patients will be (1) enrolled using the BMT CTN Advantage eClinical system and then (2) randomized in the Suvoda Interactive Response Technology (IRT) system. The IRT system will also provide the study drug supply management. Patients will be randomized to AAT versus PTM in a 1:1 ratio. The following procedures shall be followed:

Patients must be enrolled in Advantage eClinical prior to randomization in the Suvoda IRT System.

1. An authorized user at the clinical center completes the initial screening by entering patient demographics, eligibility information (consent date, inclusion/exclusion criteria) and patient's weight on the Enrollment Form in Advantage eClinical.
2. If the patient is eligible, "successful enrollment" is displayed along with a patient study ID# number and patient's weight. Information regarding participant's log-in information for the ePRO system is also included. The coordinator should print two copies of the screen: one for the patient's chart and one for the study participant.
3. **Immediately after the patient is successfully enrolled/ deemed eligible in Advantage eClinical, the authorized user must register the patient in the Suvoda IRT system for randomization to occur.** The user enters the Patient ID# assigned in eClinical, demographics (year of birth, age, and sex) and weight at time of enrollment.
4. The Suvoda IRT system will determine the patient's randomization assignment and automatically email the site's investigational pharmacist on record with the following information: Patient ID #, Visit # and the specific kits to be used to prepare the patient's assigned treatment.
5. A visit schedule based on enrollment date is displayed in Advantage eClinical for printing.

If a connection is interrupted during an enrollment session in Advantage eClinical, the process is completely canceled and logged. A backup manual enrollment system will also be available to provide for short-term system failure or unavailability. If the Suvoda IRT system is interrupted or down, the Suvoda Help Desk must be notified.

A patient is considered on the study once randomization in the IRT system is complete.

Patient must begin study drug (AAT or PTM) within 12 hours of enrollment in Advantage eClinical.

4.3 Study Monitoring

4.3.1 Follow-Up Schedule

The Follow-up Schedule for scheduled study visits is outlined in Table 4-1. The timing of follow-up visits is based on the date of enrollment. A detailed description of each of the forms and the procedures required for forms completion and submission can be found in the Data Management Handbook and User's Guide.

Criteria for Forms Submission: Criteria for timeliness of submission for all study forms are detailed in the BMT CTN 1705 Forms Guide. Forms that are not entered in Advantage eClinical within the specified time will be considered delinquent. Transplant Centers can view past due forms via Advantage eClinical. A missing form will continue to appear until the form is entered into Advantage eClinical, or until an exception is granted and entered into the Missing Form Exception File, as detailed in the Forms Guide.

Reporting Patient Deaths: The Recipient Death Information must be entered into the web-based data entry system within 24 hours of knowledge of a patient's death even if the cause of death is unknown at that time. Once the cause of death is determined, the form must be updated.

Center for International Blood and Marrow Transplant Research (CIBMTR) Data Reporting: Centers participating in BMT CTN trials must register pre- and post-transplant outcomes on all consecutive hematopoietic stem cell transplants done at their institution during their time of participation to the CIBMTR. Registration is done using procedures and forms of the Stem Cell Transplant Outcomes Database (SCTOD). (Note: Federal legislation requires submission of these forms for all US allograft recipients.) CIBMTR post- transplant Report Forms must continue to be submitted for all patients enrolled on this trial. Additionally, CIBMTR pre- and post- transplant Report Forms must also be submitted for all patients enrolled on this trial according to the randomization assigned to the patient at the time of initial registration with the CIBMTR. Long-term follow-up of patients on this study will continue through routine CIBMTR mechanisms.

4.3.2 Assessments

Assessment and/or reporting of the following is required for patients enrolled on this study. All assessments are considered standard of care unless identified below by “**”.

Pre-Enrollment

1. Performance status (Karnofsky for patients age 16 and older; Lansky for patients age 12-15.99 at the time of enrollment), history and physical exam including height and weight within 7 days prior to enrollment.
2. Complete acute GVHD staging and grading information including assessments of rash, diarrhea, nausea/vomiting, and liver abnormalities prior to enrollment.
3. Corticosteroid start date and dose (including administered dose and patient weight) prior to enrollment.
4. Liver function tests (bilirubin, alkaline phosphatase, AST, ALT) within 48 hours prior to enrollment.

5. Complete blood count (CBC) with differential and platelet count within 48 hours prior to enrollment.
6. Pregnancy test (by blood) for females of childbearing potential within 30 days prior to enrollment.

Post- Randomization (Prior to initiation of Study Drug (AAT/PTM))

1. Baseline patient-reported outcome measures prior to initiation of AAT/PTM. Only English- and Spanish-speaking patients may participate in the MDASI Health Quality of Life (HQL) component of this trial; only English-speaking patients may participate in the PROMIS HQL component. Adolescent versions should be completed by patients who are less than 18 years of age at the time of enrollment. Surveys may not be completed by surrogates.*
2. GVHD prophylaxis medication and complete acute GVHD staging and grading information including assessments of rash, diarrhea, nausea/vomiting, and liver abnormalities prior to initiation of AAT/PTM.
3. Blood research samples for serum AAT levels in peripheral blood collected pre-treatment (just prior to first dose of study drug) Note: samples will also be collected 15-45 minutes post-end of infusion.*
4. Blood research samples collected pre-treatment for serum inflammatory cytokines, GVHD biomarkers and flow cytometry.*
5. Optional stool research sample pre-treatment from consenting patients (*select centers only*).*

Post- Randomization (Treatment and Post-Treatment Follow-Up)

1. Performance status (Karnofsky for patients age 16 and older; Lansky for patients age 12-15.99) at Days 28 and 56, and at 3 months, 6 months, and 12 months.
2. Complete acute GVHD staging and grading information including assessments of rash, diarrhea, nausea/vomiting, weight and liver function tests weekly until Day 56, and 3, 6, and 12 months. Days 28 and 56 scoring must be performed by direct observation at the Transplant Center. Evaluations at other time points may be performed by clinicians familiar with assessing GVHD other than at the Transplant Center but the Transplant Center is responsible for collecting all required data. All GVHD treatment decisions must be made by the physician at the Transplant Center.
3. Liver function tests (bilirubin, alkaline phosphatase, AST, ALT) weekly until Day 56, and at 3 months, 6 months, and 12 months.
4. Chronic GVHD assessment at Days 28 and 56, and months 3, 6 and 12.
5. GVHD prophylaxis medication (if available) weekly through Day 28.
6. CBC with differential, platelet count on Days 14, 28, 56, and 86.
7. Toxicities at Day 120, 6 months and end of treatment (EOT).
8. Infections up to 3 months are reported on the event driven infection forms. Per protocol section 4.4.1 infections are anticipated events and do not require reporting as an AE/SAE.
9. Corticosteroid dose (including administered dose and patient weight) weekly until Day 56, and at months 3, 6 and 12 and/or EOT.

10. Second-line immune suppressive therapy weekly until Day 56 and at months 3, 6 and 12 and/or EOT.
11. Patient-reported outcome measures at Day 28, Day 56, and 6 months. Only English- and Spanish-speaking patients may participate in the MDASI HQL component of this trial; only English-speaking patients may participate in the PROMIS HQL component of the trial. Adolescent versions should be completed by patients who are less than 18 years of age at the time of enrollment Surveys may not be completed by surrogates.*
12. Blood research samples for serum AAT levels in peripheral blood in peripheral blood at Days 0, 8, 16, 24, 28, and 56. Samples should be drawn just prior to each study drug infusion (and within 15-45 minutes post-end of infusion for the Day 16, 28, and 56 samples). See APPENDIX B for further details.*
13. Blood research samples at Days 8, 16, 28, and 56 (or treatment discontinuation [TD] if prior to Day 56) for serum inflammatory cytokines, GVHD biomarkers and flow cytometry. The collection of required research blood samples should be coordinated with the collection of the pre-infusion blood samples for AAT level measurements. If study drug is administered before or after the indicated day, but within the treatment window (Section 2.5.1.7), the timing of the research sample can be adjusted accordingly. If it is not possible to coordinate the research sample collection, the window of collection for research blood samples is \pm 3 days.*
14. Optional stool research samples at Days 8 and 28 (or within +/- 3 days of treatment discontinuation [TD]). Stool samples from consenting patients should be collected if possible, on the target visit day indicated or within +/- 3 days of the scheduled visit. (*Select centers only*)*

Table 4-1 Required Assessments Post- Enrollment

	Pre-Enrollment	Pre-Therapy ¹	Days													EOT ² (+ 30 days)	365 (12 mos)****
			7*	14*	21*	28*	35*	42*	49*	56 *	86 (3 mos)**	120**	180 (6 mos)***				
History, physical exam, weight and height	X																
Karnofsky/Lansky Performance Status	X					X				X	X			X		X	
Pregnancy test if applicable ³	X					X				X							
Acute GVHD evaluation	X	X	X	X	X	X	X	X	X	X	X		X		X		
Liver Function Tests (alkaline phosphatase, bilirubin, AST, ALT)	X		X	X	X	X	X	X	X	X	X		X		X		
CBC with differential, platelet count	X			X		X				X	X						
Immunosuppressive drug monitoring (eg, sirolimus, tacrolimus, cyclosporine)		X	X	X	X	X	X	X	X	X	X		X	X	X		
Determination of corticosteroid dose, including administered dose and patient weight	X	X	X	X	X	X	X	X	X	X	X		X	X	X		
Chronic GVHD evaluation ⁷						X				X	X			X		X	
Toxicity assessment													X	X			
Infection monitoring ⁴		Reporting of infections at time of occurrence from time of enrollment through 3 months															
AE/SAE assessments ⁵		X	X	X	X	X	X	X	X	X	X		X ⁵	X ⁵	X ⁵		
Patient-reported outcomes ⁶ : MDASI, PROMIS		X				X				X				X			

* ± 3 days from the target day to allow for scheduling flexibility, holidays, etc.

** ± 14 days from the target day to allow for scheduling flexibility

*** ± 28 days to allow for scheduling flexibility

**** 60 days to allow for scheduling flexibility

1 Pre-therapy assessments preferably should be performed prior to enrollment, however, up to 36 hours post- enrollment is allowed.

2 End of Treatment assessments (except specimen collection) for patients that terminate treatment early will be done 30 days after the last dose of study drug. A ± 3-day window is allowed.

3 Pregnancy test (by blood) for females of childbearing potential within 30 days prior to enrollment. Serum or urine test on Day 28 and Day 56.

4 Includes anti-viral prophylaxis

5 AEs and SAEs will be reported from randomization until 30 days post last dose. Beginning at 31 days from the last dose of study drug through the end of study follow-up, SAEs deemed to be related to the study drug require reporting, and any unanticipated SAE regardless of relationship to study drug require reporting.

6 Only English- and Spanish-speaking patients are eligible to participate in the Health Quality of Life (HQOL) component of this trial. MDASI surveys to be completed by both English- and Spanish-speaking patients. PROMIS surveys to be completed by English speaking patients only. Surveys may not be completed by surrogates.

7 The Chronic GVHD Provider Survey is due at each Chronic GVHD evaluation and will record GVHD symptoms present in the last week and must be completed by a clinician on the day of the assessment.

Table 4-2 Required and Optional Research Assessments Post-Initiation of Treatment (see APPENDIX B for further details)

Type	Purpose	Day						
		Pre-Therapy ²	0	8	16	24	28	56
Required	Study drug levels ¹	X	X	X	X	X	X	
	Serum Inflammatory Cytokines and GVHD Biomarkers ⁴	X		X			X	X
	Flow Cytometry ⁴	X			X		X	X
Optional (at select centers)	Stool research samples ⁵	X		X			X	X

NOTE: Enrollment is Day 0. First dose of study drug must occur within 12 hours after enrollment and may fall on Day 0 or Day 1.

1 Samples should be drawn just prior to each study drug infusion (and also within 15 to 45 minutes post-end of infusion for the Day 0, 16, 28, and 56 samples).

2 Collect sample prior to administering study drug.

3 Sample should be collected at treatment discontinuation (TD) if that occurs prior to Day 28 (stool)/56 (blood). (Note: This is at the time that patient discontinues the study drug.)

4 The collection of required research blood samples for serum biomarkers and flow cytometry studies should be coordinated with the collection of the pre-drug infusion blood samples for AAT level measurements. If study drug is administered before or after the indicated day but within the treatment window (Section 2.5.1.7), the timing of the research sample collection can be adjusted accordingly. If not possible for some reason to not coordinate the research sample collection, the window of collection for research blood samples are \pm 3 day.

5 Stool samples being collected from consenting patients at selected centers with active Microbiome laboratories should be collected if possible on the target visit day indicated or within \pm 3 days of the scheduled visit.

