2.5.1.7 Dose and Administration

The first dose of study drug (AAT/PTM) **must be initiated as soon as possible after enrollment and must be within 12 hours of enrollment**. Each dose of study drug will be 120 mg/kg (actual weight) based on the patient's weight recorded at enrollment. Subsequent doses should be given on Days 4, 8, 12, 16, 20, 24, 28 (Table 2-1). **The patient's weight recorded at enrollment will be used to determine the dose for all infusions** (i.e., dose adjustments for changes in weight during the treatment period will not be made).

Patients that are non-responders or progress will be considered to be steroid-refractory (SR) and may start next-line therapy as described in section 2.5.3.3. Ruxolitinib is recommended for next-line therapy as it is an FDA-approved treatment for SR-GVHD.

Responding patients (CR/PR) at Day 28, compared to maximum GVHD organ staging within 72 hours prior to enrollment, that are receiving study drug alone, or study drug plus ruxolitinib, should continue to receive treatment at a dose of 120 mg/kg (actual weight) on Days 35, 42, 49, and 56 (Table 2-1). Patients who are not in CR/PR at Day 28 will not continue to receive study drug. Responding patients at Day 28 who progress after Day 28 may continue to receive weekly doses through Day 56.

Patients that receive next-line therapy other than ruxolitinib may not continue receiving study drug unless approval is granted by the BMT CTN 1705 Protocol Chairs.

Table 2-1 Study Drug Schedule

	Day											
	0 ¹	4	8	12	16	20	24	28	35	42	49	56
All patients	X	X	X	X	X	X	X	X				
CR/PR (VGPR) patients only									X	X	X	X

¹ Enrollment is Day 0, First dose of study drug must occur within 12 hours after enrollment and may fall on Day 0 or Day 1.

Patients can receive study drug (AAT/PTM) as either an inpatient or outpatient. All subsequent treatments will have a window of \pm 3 days to allow for efficient scheduling of patients for holidays/weekends/etc. Following administration of the first or second dose, adjusting future infusions to accommodate a Monday/Thursday or Tuesday/Friday schedule is encouraged.

Infusion Rate: AAT/ PTM should be administered at a rate not exceeding 0.08 mL/kg body weight/minute. If adverse events occur, the rate should be reduced, or the infusion interrupted until the symptoms subside. The infusion may then be resumed at a rate tolerated by the subject.

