2 STUDY SCHEMA AND PATIENT ASSESSMENT SCHEDULE

2.1 STUDY SCHEMA

2.2 SCHEDULE OF ASSESSMENTS

Table 1: Required Assessments Post-Enrollment

	Pre-Enrollment	Pre-Therapy ¹	Days											EOT ² (+ 30 days)	12 mos****
			7*	14*	21*	28*	35*	42*	49*	56 *	86 (3 mos)**	120**	6 mos***		
History, physical exam, weight and height	X														
Karnofsky/Lansky Performance Status	X					X				X	X		X		X
Pregnancy test if applicable ³	X				X					X					
Acute GVHD evaluation	X	X	X	X	X	X	X	X	X	X	X		X		X
Liver Function Tests (alkaline phosphatase, bilirubin, AST, ALT)	X		X	X	X	X	X	X	X	X	X		X		X
CBC with differential, platelet count	X			X		X				X	X				
Immunosuppressive drug monitoring (e.g., sirolimus, tacrolimus, cyclosporine)		X	X	X	X	X	X	X	X	X	X		X	X	X
Determination of corticosteroid dose, including administered dose and patient weight	X	X	X	X	X	X	X	X	X	X	X		X	X	X
Chronic GVHD evaluation ⁷						X				X	X		X		X
Toxicity assessment													X	X	
Infection monitoring ⁴			Reporting of infections at time of occurrence from time of enrollment through 3 months												
AE/SAE assessments ⁵			X	X	X	X	X	X	X	X	X		X ⁵	X ⁵	X ⁵
Patient-reported outcomes ⁶ : MDASI, PROMIS		X				X				X			X		

Notes:

* +/- 3 days from the target day to allow for scheduling flexibility, holidays, etc.

** +/- 14 days from the target day to allow for scheduling flexibility

*** +/- 28 days to allow for scheduling flexibility

**** 60 days to allow for scheduling flexibility

1 Pre-therapy assessments preferably should be performed prior to enrollment; however, up to 36 hours post-enrollment is allowed.

2 End of Treatment assessments (except specimen collection) for patients that terminate treatment early will be done 30 days after the last dose of study drug. A +/- 3-day window is allowed.

3 Pregnancy test (by blood) for females of childbearing potential within 30 days prior to enrollment. Serum or urine test on Day 28 and Day 56.

4 Includes anti-viral prophylaxis

5 AEs and SAEs will be reported from randomization until 30 days post last dose. Beginning at 31 days from the last dose of study drug through the end of study follow-up, SAEs deemed to be related to the study drug require reporting, and any unanticipated SAE regardless of relationship to study drug require reporting.

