7 STATISTICAL METHODOLOGY

7.1 GENERAL GUIDELINES

Counts and percentages will be used to describe categorical variables, while the number of subjects (N), median, mean, standard deviation, interquartile range and range will be used to summarize continuous variables.

The study day for most efficacy and safety assessments will be computed in reference to the date of randomization, with the date of randomization defined as Study Day 0 for each patient. For all assessments, the (Study) Day will be calculated as (assessment date – randomization date). Unless otherwise specified, the visit window will be defined similarly to those specified in the protocol with the target day calculated in reference to the date of randomization. For outcomes where data are summarized in reference to a different date, such as treatment initiation, the assessment time point is clarified explicitly.

For each patient-reported outcome, the baseline value is defined as the outcome score assessed at the Pre-Therapy visit on the schedule of assessments (**Section 2.2**). For all other variables, unless otherwise specified, the baseline value is defined as the last available measurement prior to the first infusion of study drug if the measurement time was collected and the last available measurement before or on the date of the first infusion of study drug if the measurement time was not collected.

Hypothesis testing for the primary endpoint's analysis is one-sided, evaluating the superiority of AAT to PTM for Day 28 overall response, at a 2.5% significance level. The testing for secondary endpoints will be two-sided at a 5% significance level and is equivalent to assessment by two one-sided tests, each at a 2.5% level. Testing of exploratory endpoints will be two-sided at a 1% significance level. **Table 14** summarizes the endpoints to be analyzed for each analysis population.

A hierarchical testing procedure will be employed to ensure control of the familywise type I error rate at a one-sided, 2.5% level when evaluating the primary and key secondary endpoints of interest. A gatekeeping approach will be used with the following tests of superiority of AAT to PTM for the corresponding endpoints:

1. Overall Response at Day 28: The Wald test from the primary analysis as specified in **Section 7.4.3.1** (one-sided at 2.5% level)

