7.4.3.4 SUPPLEMENTARY ANALYSES

Two supplementary analyses will investigate the potential influence of other variables on the primary analysis' outcome in the ITT population. Two logistic mixed models will be fitted with Day 28 overall response as the outcome. One model will have fixed effects of treatment arm, MN risk, age (under 18 years vs. 18 years or older), and disease type (malignant vs. non-malignant) and a random effect of center-group; the second will also include these covariates in addition to the MAGIC biomarker risk score (1 vs. 2 vs. 3). If no patients under 18 years old are enrolled and randomized, the fixed effect for age will be omitted from the model. The results from the second model may be presented in a separate report depending on the biomarker data availability.

In addition to these protocol-specified supplementary analyses, an additional supplementary analysis will assess Day 28 overall response in comparison to the aGVHD organ staging at initiation of AAT/PTM (i.e., aGVHD organ staging collected at pre-therapy visit if available, and the maximum GVHD organ staging within 72 hours prior to enrollment if not available). The analysis population will include the mITT patients, i.e., those who initiate their assigned study therapy. A logistic mixed model will evaluate the effect of treatment arm on Day 28 overall response with adjustment for treatment center and MN risk as specified in Section 7.4.1.1.

Moreover, the effects of duration from the initiation of corticosteroid to the initiation of IMP (<= 24 hours vs. 24-48 hours vs. 48-72 hours vs. 72 hours or more) and dose of corticosteroid on Day 28 post-randomization (>= 2mg/kg/day vs. 1.00-1.99 mg/kg/day vs. 0.26-1.00 mg/kg/day vs. 0.25 mg/kg/day or less, prednisone-equivalent) on Day 28 overall response will be evaluated using logistic mixed models that adjust for treatment center-group and MN risk. These analyses will use the mITT population.

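### Footnote 1 of the assessment schedule lets pre-therapy GVHD staging and patient-reported outcomes follow the first infusion, contradicting Protocol 4.3.2, and the SAP baseline rules do not screen such values out

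*Protocol*

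**What the plan says.** **Assessment window.** Footnote 1 is attached to the Pre-Therapy column of Protocol Table 4-1, which includes the acute GVHD evaluation and the PROs (MDASI, PROMIS): "Pre-therapy assessments preferably should be performed prior to enrollment, however, up to 36 hours post- enrollment is allowed". Footnote 1 of SAP Table 1 (section 2.2) carries the same allowance: "Pre-therapy assessments preferably should be performed prior to enrollment; however, up to 36 hours post-enrollment is allowed".

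**First dose.** Protocol 4.2: "Patient must begin study drug (AAT or PTM) within 12 hours of enrollment in Advantage eClinical". Protocol 2.5.1.7 says the same of the first dose: "must be initiated as soon as possible after enrollment and must be within 12 hours of enrollment".

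**Order of events.** Protocol 4.3.2, in its list of items due after randomization but before study drug, begins with "Baseline patient-reported outcome measures prior to initiation of AAT/PTM". Its next item puts complete acute GVHD staging under the same condition.

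**SAP baselines.** SAP 7.1 states for PROs that "the baseline value is defined as the outcome score assessed at the Pre-Therapy visit on the schedule of assessments". For all other variables its default is the most recent value before the first infusion, or on or before the infusion date if no clock time was collected. SAP 7.4.3.4 plans a supplementary analysis in the modified intention-to-treat population that measures Day 28 response against staging when AAT/PTM starts. It takes that staging as "aGVHD organ staging collected at pre-therapy visit if available", and otherwise uses the worst staging in the 72 hours before enrolment.

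**The concern.** A baseline should precede the treatment whose effect is measured against it. Here one rule requires that order and another waives it. The SAP then takes its baseline from the visit, not from the time relative to infusion. A site that follows the footnote can record a so-called pre-therapy value after study drug without breaching the schedule, and the analysis would use it.

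Two analyses depend on these values. The supplementary response analysis is the only one that moves the response reference from the pre-enrolment maximum to the start of study drug, after up to 72 hours of steroids. If its reference is taken after the infusion, it no longer describes the patient at treatment start. The PRO models in SAP 7.6.8 adjust for the baseline score, so a late score means adjusting for a post-treatment value.

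Late PRO scores are plausible in practice. PROs are collected electronically (Protocol 3.3.8), and log-in details are issued only at successful enrolment (Protocol 4.2, step 2). The survey therefore competes for time with a first dose that is due as soon as possible.

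**Working it through.** The plan states no figure for the gap between first dose and pre-therapy assessment, so there is none to reproduce. The check is arithmetic on the windows, followed by tracing where the values are used.

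**1. Largest permitted lag.** Inputs: assessment allowed until hour 36 (footnote 1); first dose at hour *t*, with *t* between 0 and 12 (Protocol 2.5.1.7 and 4.2). Largest lag after dose = 36 − *t*. Share of the 36-hour post-enrolment window that falls after the dose = (36 − *t*)/36.

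| First dose (hour) | Largest lag (h) | Share of window after dose |
|---|---|---|
| 0 | 36 | 100% |
| 3 | 33 | 92% |
| 6 | 30 | 83% |
| 9 | 27 | 75% |
| 12 | 24 | 67% |

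For any patient dosed on time, hours 12 to 36 (36 − 12 = 24 hours) are post-dose. That part of the allowance cannot be reconciled with Protocol 4.3.2 by reading the two together. A lag of 24 hours or more needs an assessment at or after hour *t* + 24, which leaves the last 12 hours of the window for a dose at hour 0 and only its end point for a dose at hour 12.

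**2. Is the dose complete by then?** Dose 120 mg/kg and rate limit 0.08 mL/kg/min (Protocol 2.5.1.7), solution 50 mg/mL (Protocol 2.5.1.2). Volume = 120/50 = 2.4 mL/kg; shortest infusion = 2.4/0.08 = 30 minutes. A late value can therefore follow a complete infusion.

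**3. What a late staging value can change.** CR is stage 0 in all evaluable organs at the assessment (Protocol 3.1.1), so it does not depend on baseline. PR, mixed response, no response and progression do. As an illustration, take one involved organ at stage 2 before infusion, stage 1 at a late pre-therapy visit and stage 1 on Day 28. This is PR against the first reference and no response against the second. If the late value were stage 3 and Day 28 stage 2, the call would move the other way, from no response to PR.

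**4. What a late PRO score can change.** Most PROMIS items in Protocol Appendix F ask about the past 7 days, that is 168 hours. At the permitted extremes the post-dose part of the recall period is 24/168 = 14% to 36/168 = 21%. Items 1 and 10 to 13 state no recall period, and the MDASI text is not in the documents.

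**5. What is not exposed.** The primary endpoint uses the worst staging in the 72 hours before enrolment (Protocol 3.1, SAP 6.1). Power uses no pre-therapy value: 68 per arm, 50% versus 75%, one-sided 2.5% gives 0.862, against the stated 86%. Research blood and stool baselines are tied to collection before the infusion (Protocol Table 4-2 footnote 2, Appendix B).

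**The case against.** The best defence is that the intended design is clear. The column is labelled Pre-Therapy, Protocol 4.3.2 puts both assessments before study drug, and SAP 7.4.3.4 describes its reference as staging at initiation of AAT/PTM. On this view one footnote is loosely worded and a careful programmer would take only pre-infusion values. This stands as to intent: a reader might infer that post-drug baselines are a deliberate design choice, and Protocol 4.3.2 rules that out. It does not settle the matter, because the SAP copies the footnote, exempts PROs from its before-infusion default, and triggers the staging fallback only when the visit value is unavailable, not when it is late.

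A reader might also infer that late staging lowers the AAT arm's starting stage and biases towards no difference the sole check on improvement during prior steroids. The documents do not support that:

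- SAP 7.4.3.4 also models response by the interval from steroid start to study drug, and neither document assigns the re-baselined analysis this purpose.
- Protocol 1.6.5 expects high AAT levels soon after dosing, but from simulated serum concentrations. Nothing shows an organ stage changing within 24 to 36 hours of one infusion, and Protocol 2.5.3.3 allows no progression call before 72 hours.
- Steroids continue in both arms during the window, and step 3 shows that a call can move either way.

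For PROs, the 7-day recall of most PROMIS items dilutes the effect. It does not remove it.

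**Conclusion.** The contradiction is real and the SAP carries it into two analyses: the supplementary response analysis from treatment start, through calls other than CR, and the exploratory PRO analyses. At the permitted extreme a baseline can fall 24 to 36 hours after the first dose, depending on when the dose is given. The share of patients affected could be anything from none to all of those whose pre-therapy visit follows the infusion, and neither the size nor the direction of any bias can be derived from the documents.

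It would be wrong to infer that the trial's conclusion is at risk. Efficacy is judged on the primary analysis alone (SAP 7.4.3.5), and tests outside the hierarchy are descriptive (SAP 7.1). Severity is minor. The lag figures assume that the first dose is given within the 12-hour limit and that sites follow the footnote as written.

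**What to change.** 1. Reconcile footnote 1 of Protocol Table 4-1 and SAP Table 1 with Protocol 4.3.2, so that pre-therapy staging and PROs are completed before the first infusion starts. The dosing deadline is not part of this change.
2. In SAP 7.4.3.4, use pre-therapy staging only if it was taken before the first infusion, or on or before the infusion date where no time was collected, as SAP 7.1 already does for other variables. Otherwise use the 72-hour fallback already named there.
3. In SAP 7.1, put the same condition on PRO baselines. Treat later scores as a missing baseline, with a sensitivity analysis that retains them.
4. Report the number of post-dose Pre-Therapy values by arm.

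**Cost.** Wording in two footnotes and two SAP sections, plus a date and time check in programming. SAP section 1 allows revision before the database hard lock, so the SAP change need not wait for a protocol amendment. There are three drawbacks. Patients moved to the fallback are again compared with the primary endpoint's own reference. Some PRO baselines become missing, and SAP 7.9 assumes that such missingness is random, which may fail for patients too ill to answer before dosing; hence the sensitivity analysis. The same-day rule can still admit a post-dose value taken on the infusion date.
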